5.2 Procedural and In-Hospital Experience Endpoints

Outcomes related to the Boston Scientific S-ICD procedure such as, but not limited to, type of anesthesia, implant duration, use of fluoroscopy or X-ray and length of hospital stay will be summarized as described in section 5.1 based on the type of variable, continuous or categorical.

5.3 Registry Endpoints

- **Registry Endpoint 1:** 30-Day S-ICD Complication-Free Rate*, will be summarized as the number of subjects and the percentages relative to the Registry population including the corresponding 95.0% two-sided exact binomial confidence interval.
- **Registry Endpoint 2:** 360-Day S-ICD Complication-Free Rate*, will be analyzed using the Kaplan-Meier (KM) estimate and its corresponding 95.0% confidence interval based on Peto estimate of the standard error.
- **Registry Endpoint 3:** The Percentage of Inappropriate Shocks for AF/SVT, will be analyzed by dividing the number of patients who received at least one inappropriate shock over the total number implanted patients. The mean, median and inter-quartile follow-up time will also be presented.

**Type I Complications will be considered to count towards the complication rate endpoints (see section 10.2). Events related to normal device function e.g. battery deletion within acceptable margins, will not count against the endpoints*

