3.2 Registry Endpoints

The primary Registry endpoints will be examined using the following metrics:

- **Registry Endpoint 1:** Perioperative (30 days post implant) S-ICD System Complication Free Rate

Boston Scientific
EFFORTLESS S-ICD Study Protocol
90904925, Rev/Ver AB

Page 14 of 52

- **Registry Endpoint 2:** 360 day S-ICD System Complication Free Rate
- **Registry Endpoint 3:** Percentage of Inappropriate Shocks for AF/SVT

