5.5 Additional Data Analysis

- Conversion efficacies for both induced and spontaneous episodes and first shock will be summarized as the number of subjects and the percentages relative to the Registry population including the corresponding 95.0% two-sided exact binomial confidence interval.
- Clinical event rates will be presented as 30-day event rates as summarized by number of subjects and its corresponding percentage and 95.0% two-sided exact binomial confidence interval and long-term rates as either linear rates or Kaplan-Meier freedom from event.
- Linearised rate of inappropriate therapies will also be calculated by dividing the total number of inappropriate therapies by the total number of follow-up patient years. Linearised rate calculation will only be initiated if a minimum of 100 patient years have been reached.
- Kaplan-Meier estimates and curves for therapy delivered including:
 - Time to first therapy delivered (both appropriate and inappropriate)
 - Time to first appropriate therapy delivered
 - Time to first inappropriate therapy delivered
- Re-occurrence of inappropriate shock therapy after reprogramming will be calculated using the total number of additional inappropriate shocks recorded from patients who have previously experienced at least one inappropriate shock and had their S-ICD reprogrammed in an attempt to resolve the issue (adjustments may include but are not limited to, changing sensing vector, adjustment to ECG gain, reprogramming of shock rates)
- Considering that patients who are prospectively enrolled in this Registry will come from the investigator's general ICD population, it is a priori unknown how many will be primary versus secondary prevention patients. Analyses will be conducted for primary versus secondary prevention, for inclusion in separate cost-effectiveness models for those populations.

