5.6 Sample Size Determination

As part of an observational Registry, the target sample size of 1000 was not derived through a power driven hypothesis testing. Tables 1 & 2 below demonstrate the corresponding confidence interval length for estimated values for Registry Endpoints 1 and 2 at various sample size time points. The maximum sample size presented is 900 to allow up to 10% attrition rate.

Table 1: 30-Day Complication Free Rate Estimated Values & 95.0% Exact Conf. Interval

Estimated Value	Sample Size								
	100	200	300	400	500	600	700	800	900
90%	-7.6%/+5.1%	-5.0%/+3.8%	-4.0%/+3.2%	-3.4%/+2.8%	-3.0%/+2.5%	-2.7%/+2.3%	-2.5%/+2.1%	-2.3%/+2.0%	-2.1%/+1.9%
91%	-7.4%/+4.8%	-4.9%/+3.6%	-3.8%/+3.0%	-3.2%/+2.6%	-2.9%/+2.4%	-2.6%/+2.2%	-2.4%/+2.0%	-2.2%/+1.9%	-2.1%/+1.8%
92%	-7.2%/+4.5%	-4.7%/+3.4%	-3.7%/+2.8%	-3.1%/+2.5%	-2.7%/+2.2%	-2.5%/+2.0%	-2.3%/+1.9%	-2.1%/+1.8%	-2.0%/+1.7%
93%	-6.9%/+4.1%	-4.5%/+3.1%	-3.5%/+2.6%	-3.0%/+2.3%	-2.6%/+2.1%	-2.3%/+1.9%	-2.1%/+1.8%	-2.0%/+1.7%	-1.9%/+1.6%
94%	-6.6%/+3.8%	-4.2%/+2.9%	-3.3%/+2.4%	-2.8%/+2.1%	-2.5%/+1.9%	-2.2%/+1.8%	-2.0%/+1.6%	-1.9%/+1.5%	-1.8%/+1.5%
95%	-6.3%/+3.4%	-4.0%/+2.6%	-3.1%/+2.2%	-2.6%/+1.9%	-2.3%/+1.7%	-2.1%/+1.6%	-1.9%/+1.5%	-1.7%/+1.4%	-1.6%/+1.3%
96%	-5.9%/+2.9%	-3.7%/+2.3%	-2.9%/+1.9%	-2.4%/+1.7%	-2.1%/+1.5%	-1.9%/+1.4%	-1.7%/+1.3%	-1.6%/+1.2%	-1.5%/+1.2%
97%	-5.5%/+2.4%	-3.4%/+1.9%	-2.6%/+1.6%	-2.2%/+1.4%	-1.9%/+1.3%	-1.7%/+1.2%	-1.5%/+1.1%	-1.4%/+1.1%	-1.3%/+1.0%
98%	-5.0%/+1.8%	-3.0%/+1.5%	-2.3%/+1.3%	-1.9%/+1.1%	-1.6%/+1.0%	-1.5%/+1.0%	-1.3%/+0.9%	-1.2%/+0.9%	-1.1%/+0.8%
99%	-4.4%/+1.0%	-2.6%/+0.9%	-1.9%/+0.8%	-1.5%/+0.7%	-1.3%/+0.7%	-1.2%/+0.6%	-1.0%/+0.6%	-1.0%/+0.6%	-0.9%/+0.5%

Exact confidence interval based on the mathematical relationship between the F distribution and cumulative binomial distribution (Fleiss et al (2003)), Statistical Methods for Rate and Proportion, 3rd Edition

Table 2: 360-Day Complication Free Rate Estimated Values & 95.0% KM Conf. Inter. (Peto)

Estimated Value	Sample Size								
	100	200	300	400	500	600	700	800	900
70%	± 9.0%	± 6.4%	± 5.2%	± 4.5%	± 4.0%	± 3.7%	± 3.4%	± 3.2%	± 3.0%
71%	± 8.9%	± 6.3%	± 5.1%	± 4.4%	± 4.0%	± 3.6%	± 3.4%	± 3.1%	± 3.0%
72%	± 8.8%	± 6.2%	± 5.1%	± 4.4%	± 3.9%	± 3.6%	± 3.3%	± 3.1%	± 2.9%
73%	± 8.7%	± 6.2%	± 5.0%	± 4.4%	± 3.9%	± 3.6%	± 3.3%	± 3.1%	± 2.9%
74%	± 8.6%	± 6.1%	± 5.0%	± 4.3%	± 3.8%	± 3.5%	± 3.2%	± 3.0%	± 2.9%
75%	± 8.5%	± 6.0%	± 4.9%	± 4.2%	± 3.8%	± 3.5%	± 3.2%	± 3.0%	± 2.8%

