- Rate of electrode failures and revisions, including the reason for revision
- Rate of device failures and revisions, including the reason for revision
- Rate of complications related to the S-ICD replacements
- Appropriate therapy for VT/VF
- Inappropriate shock therapy (e.g. atrial fibrillation, supraventricular tachycardia)

The following observational data will be collected and analysed additionally to the main study:

- Generator changes/electrode revisions
- VF induction testing at replacement
- Complications associated with S-ICD to TV-ICD change
- Additional invasive interventions (e.g. VT ablation)
- Use of anti-arrhythmic drugs
- Ventricular cycle length of episodes
- Duration (non-sustained episodes)

Patients enrolled in the Sub-Study must meet all inclusion criteria and none of the exclusion criteria as described below.

Inclusion Criteria

1. Subjects who are actively enrolled in the EFFORTLESS S-ICD Registry OR Subjects who completed the 5-year follow-up in the EFFORTLESS S-ICD Registry. All clinical events, spontaneous and induced episode data and system replacement or revision data since the last EFFORTLESS S-ICD Annual Follow-Up of the main study must be available in medical files or equivalent.
2. Subjects who are actively implanted with an S-ICD pulse generator (SQ-RX, EMBLEM or EMBLEM MRI) and an S-ICD electrode (Q-TRAK or EMBLEM) or any other future commercial available versions
3. Willing and able to provide written informed consent or have informed consent as provided by a legal representative and willing to participate in all testing and follow-ups as described the Sub-Study protocol
4. Age 18 or above, and of legal age to give informed consent specific to national laws

Exclusion Criteria

1. Subjects with device replacement from the S-ICD to a transvenous ICD
2. Subjects with unipolar pacemakers or implanted devices that revert to unipolar pacing
3. Subjects that are participating in any other investigational study that may interfere with interpretation of the Registry results, without the written approval of Boston Scientific

Once a patient is enrolled in the Sub-Study, the visit schedule according to Table 8 must be followed. Patients, who have still been actively enrolled in the main EFFORTLESS S-ICD Registry will be waived from the visit requirements as described in Table 3 (Section 7.1) and will be followed-up according to Table 8 only.

Table 8: Summary of information requested for the Sub-Study

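### Registry Endpoint 3 (inappropriate shocks for AF/SVT) is a crude proportion with no stated horizon or named interval, and no time-based analysis is specified for AF/SVT; a cheap clarification, with little effect at complete 60-month follow-up

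*Combined protocol and SAP*

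**What the plan says.** Section 3.2 introduces its list of three endpoints with "The primary Registry endpoints will be examined using the following metrics"; the percentage of inappropriate shocks for AF/SVT is the third.

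Section 5.3 gives the analyses. Endpoint 1 is a 30-day percentage with an exact binomial 95% interval. Endpoint 2 is a 360-day Kaplan-Meier estimate with a 95% interval from the Peto standard error. Endpoint 3 "will be analyzed by dividing the number of patients who received at least one inappropriate shock over the total number implanted patients", followed by: "The mean, median and inter-quartile follow-up time will also be presented". It has no time point and no interval.

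Other relevant text:

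- **Section 5.6.** The precision tables are for "Registry Endpoints 1 and 2 at various sample size time points". They stop at 900 patients "to allow up to 10% attrition rate".
- **Section 5.5.** It plans a linearised rate of inappropriate therapies and a Kaplan-Meier curve for "Time to first inappropriate therapy delivered". Neither is limited to AF/SVT, and Section 3.2.1 defines inappropriate therapy as a shock for any rhythm that is not VT/VF.
- **Section 5.7.** Drop-outs are censored in time-to-event analyses.
- **Section 5.8.** Intervals, where used, are at the two-sided 5% level; no method is named.
- **Sections 4.1, 4.3 and 7.5.** Data are collected to 60 months from implant, and a patient completes at 1800 days or more.
- **Appendix E.** Sub-Study patients still active in the main Registry "will be waived from the visit requirements as described in Table 3 (Section 7.1) and will be followed-up according to Table 8 only".

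**The concern.** A crude proportion has a clear time meaning only when everyone is observed for the same period, or leaves for a reason that belongs to the outcome definition. Section 5.3 does not state the period. A summary of follow-up describes unequal observation but does not adjust for it. The time-based analyses that would adjust for it are planned for inappropriate therapy of any cause, not for the AF/SVT event that this endpoint names.

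Section 1.3 says that a better system must show fewer inappropriate therapies for AF/SVT, and Endpoint 3 is the Registry endpoint that speaks to this. Readers will set the percentage beside figures from transvenous systems and need to know the period it covers. Section 5.0 makes the analyses descriptive, so no test, power figure or error rate is at stake; only the meaning of one reported percentage is.

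**Working it through.** **The plan's own figures.** No figure is stated for Endpoint 3. The tables for the other two endpoints are sound. For 95% complication-free at n = 900, the exact interval for 855/900 is 93.4% to 96.3%, which is the -1.6/+1.3 in Table 1. All 90 cells of Table 1 reproduce to rounding, as do the 36 cells checked in Table 2 (rows 70, 80, 85 and 90%).

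**Inputs**

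- Target of 1000 patients, 60 months from implant, Registry duration 108 months: Sections 4.1 to 4.3.
- Attrition of 10%: Section 5.6, where it belongs to the 30-day and 360-day tables. Applying it to 60 months is an assumption.
- Hazard of first AF/SVT shock, h = 2, 4 or 6% per year, constant: an assumption. The documents' only benchmark is in Section 1.2: inappropriate therapy of any cause in close to 10% of transvenous patients, with no period given. The lowest hazard (9.5% at 5 years) is nearest to it; the other two are high.

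**(a) Closure with complete 60-month follow-up.** The 5-year risk is 1 - exp(-5h). The exit hazard is c = -ln(0.9)/5 = 0.0211 per year. The crude proportion is h/(h+c) × [1 - exp(-5(h+c))].

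| h | 5-year risk | crude | shortfall |
|---|---|---|---|
| 2%/yr | 9.5% | 9.0% | 0.5 points |
| 4%/yr | 18.1% | 17.2% | 0.9 points |
| 6%/yr | 25.9% | 24.7% | 1.3 points |

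This is the shortfall if every exit is loss to follow-up. If every exit is death, the crude figure is itself the cumulative incidence and the shortfall is zero. For scale, the exact 95% interval is 7.3% to 10.9% at 90/1000 and 14.9% to 19.7% at 172/1000, so sampling error exceeds the shortfall.

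**(b) What the missing cut-off is worth.** An average of 8 years with 5 years added puts Sub-Study entry at about year 3. Suppose 200 of 1000 patients are counted to year L, the rest to year 5, with no attrition: 0.8 × [1 - exp(-5h)] + 0.2 × [1 - exp(-Lh)].

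| h | L = 3 | L = 5 | L = 8 |
|---|---|---|---|
| 2%/yr | 8.8% | 9.5% | 10.6% |
| 4%/yr | 16.8% | 18.1% | 20.0% |
| 6%/yr | 24.0% | 25.9% | 28.4% |

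L = 5 is the natural reading, since the Sub-Study lists its own inappropriate-shock analysis and Table 8 still collects episodes.

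**(c) Only if reported when the last patient reaches 12 months.** 108 - 60 = 48 months of accrual, assumed uniform, gives follow-up of 1 to 5 years. The crude proportion is 1 - [exp(-h) - exp(-5h)]/(4h) = 5.8%, 11.2%, 16.3%. The 1-year risks are 2.0%, 3.9%, 5.8% and the 5-year risks 9.5%, 18.1%, 25.9%, so the crude figure is neither; it is 0.61 to 0.63 of the 5-year risk.

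The follow-up summary does not repair this. Keep the 5-year risk at 18.1% and the mean and median follow-up at 3 years, and change only the timing (hazard in year 1, then later):

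- 2%, then 4.5%: crude 10.3%
- 4% throughout: crude 11.2%
- 12%, then 2%: crude 14.8%

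**The case against.** The strongest reply is that the plan supplies most of what seems missing. The common 60-month window gives Endpoint 3 a horizon in substance at closure. Section 5.8 sets the level for any interval. Section 5.5 already plans Kaplan-Meier curves, and its list is open-ended, so an AF/SVT curve is not ruled out. In a descriptive single-arm registry, a crude percentage with follow-up time beside it is a legitimate summary. Most of this stands, and it limits the weight of the point. What remains is that 5.3 states no horizon or interval for this endpoint alone of the three, and that no AF/SVT-specific time-based estimate is specified.

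Four stronger readings are tempting, and the documents do not support them.

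- **That the endpoint counts inappropriate shocks of any cause.** The numerator does not repeat the AF/SVT limit, but the endpoint's title carries it and Section 3.0 words the measure as patients with inappropriate shocks for AF and/or SVT. The synopsis overview, which speaks of a percentage of shocks, needs only a minor correction.
- **That Sub-Study years will be pooled into the endpoint, or that patients drop out of it at Sub-Study entry.** Inappropriate shock therapy is a secondary analysis of the Sub-Study, listed as additional to the main endpoints. That argues against counting to year 8. Table 8 collects episodes, which argues against stopping at year 3. No sentence states the cut-off, but 60 months is the natural one.
- **That early reporting is planned, so the figure will be about 0.6 of the 5-year risk.** The cues are weak. The time points in 5.6 concern Endpoints 1 and 2. "Linearised rate calculation will only be initiated if a minimum of 100 patient years have been reached" governs a rate that already allows for time. Scenario (c) also ignores retrospective patients implanted since June 2009, whose follow-up may be longer.
- **That death and explant bias the crude figure.** If both are treated as competing events, they do not; only withdrawal and loss to follow-up can.

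**Conclusion.** The point holds as a cheap improvement in specification. Endpoint 3 has no stated horizon and no named interval, follow-up does not enter the estimate, and the time-based analyses in 5.5 are not specified for AF/SVT.

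At closure the numerical consequence is small: at most about 0.5 to 1.3 points below the 5-year risk, and zero if attrition is all death. This rests on assumed constant hazards of 2 to 6% per year and on carrying the 10% attrition forward to 60 months. The departure becomes material only if the figure is reported while follow-up is incomplete. The documents neither direct nor exclude that, so the larger figures in (c) are conditional and not a forecast.

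**What to change.** Amend Section 5.3 for Endpoint 3:

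1. Define the event, per patient, as the first inappropriate shock adjudicated as due to AF/SVT, and use the same per-patient wording in the synopsis overview.
2. Report a time-to-event estimate at 360 days and 60 months from implant with a 95% interval. Use cumulative incidence with death and permanent explant as competing events and other exits censored, or Kaplan-Meier as for Endpoint 2 with the handling of death and explant stated.
3. Count follow-up to 60 months from implant, whether recorded under Table 3 or Table 8.
4. Keep the crude percentage with the follow-up summary, labelled as descriptive.

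The cost is a wording amendment and one further survival analysis. Adjudication of endpoint-related episodes (4.4), Kaplan-Meier methods (5.5) and censoring (5.7) are already planned, and no new data are needed. The downside is two figures for one endpoint, which must be clearly labelled.

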5.7 Missing Data

Every effort will be utilized to minimize missing data. The number of data for each variable presented will be stated. The number of patients withdrawing from the Registry will be presented with their corresponding time of discontinuation. Time-to-event drop-outs will be censored, consistent with the Kaplan-Meier approach. Any data outside follow-up time period tolerance that was used for analysis will be noted with results presented.

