7.5 Annual Follow-Ups

After all scheduled and unscheduled follow-ups have been collected for the first 360 days of the Registry, data will continue to be collected once annually until either 60

months of patient data have been collected; the patient withdraws from the Registry (or is withdrawn including for reasons of death) or is Lost to Follow-Up.

To aid with centre planning, this annual follow-up should be timed to occur 24, 36, 48 months +/- 90 days and 60 month +90 days post implantation date. Once a patient has a follow-up time of at least 1800 days post implant date they will have completed the study.

All the system-related events and hospitalizations that occurred during the period prior to the annual data follow up, will be collected.

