9.0 Potential Risks and Benefits

9.1 Analysis of Risks

A complete list of anticipated cautions, warnings and potential clinical events is included in the User's Manual. The risks associated with the use of the S-ICD System are comparable to those associated with the use of any other currently available single or dual chamber ICD; however, the S-ICD System is completely subcutaneous, and therefore, risks associated with the placement of transvenous leads are not applicable.

There are no additional risks for the patients, who are participating in the Sub-Study (see Appendix E) compared to the main study.

Risks associated with the S-ICD System and implant procedure may include, but are not limited to the following:

- Acceleration/induction of atrial or ventricular arrhythmia
- Adverse reaction to induction testing
- Allergic/adverse reaction to system or medication
- Bleeding
- Conductor fracture
- Cyst formation
- Death
- Delayed therapy delivery
- Discomfort or prolonged healing of incision
- Electrode deformation and/or breakage
- Electrode insulation failure
- Erosion/extrusion
- Failure to deliver therapy
- Fever
- Hematoma/seroma
- Hemothorax
- Improper electrode connection to the device
- Inability to communicate with the device
- Inability to defibrillate or pace
- Inappropriate post-shock pacing
- Inappropriate shock delivery
- Infection
- Keloid formation
- Migration or dislodgement
- Muscle/nerve stimulation
- Nerve damage
- Pneumothorax
- Post-shock/post-pace discomfort
- Premature battery depletion
- Random component failures
- Stroke
- Subcutaneous emphysema
- Surgical revision or replacement of the system
- Syncope
- Tissue redness, irritation, numbness or necrosis

If any adverse events occur, invasive corrective action and/or S-ICD System modification or removal may be required.

Patients, who receive an S-ICD System may develop psychological disorders that include, but are not limited to, the following:

- Depression/anxiety
- Fear of device malfunction
- Fear of shocks
- Phantom shocks

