10.0 Clinical Events

10.1 Clinical Event Definitions

Adverse Event – Any untoward medical occurrence in a subject. This definition does not imply that there is a relationship between the adverse event and the system under investigation.

Adverse Device Effect- Any untoward or unintended response to a medical device. This definition includes any event resulting from insufficiencies or inadequacies in the instructions for use or deployment of the device. It also includes any event that is a result of user error.

Serious Adverse Event – A clinical event that:

- Led to a death;
- Led to a serious deterioration in the health of the subject that:
 - resulted in a life-threatening illness or injury,
 - resulted in a permanent impairment of a body structure or a body function,
 - required in-patient hospitalization or prolongation of existing hospitalization,
 - resulted in medical or surgical intervention to prevent permanent impairment to body structure or a body function;
- Led to fetal distress, fetal death or a congenital abnormality or birth defect.

Serious Adverse Device Effect- An adverse device effect that has resulted in any of the consequences characteristic of a serious adverse event or that might have led to any of these consequences if suitable action had not been taken or intervention had not been made or if circumstances had been less opportune

Observation – A clinical event that does not result in invasive intervention. Examples of such non-invasive intervention include, system reprogramming, antibiotic treatment of pocket infection, or change in medications.

Complication – A clinical event that results in invasive intervention. Examples of such invasive intervention include surgical intervention, system repositioning, and system explant.

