10.2 Classification of Clinical Events

All clinical events will be categorized as observations or complications. In addition, clinical events will be classified by type as shown below.

- Type I: Caused by the S-ICD System
- Type II: Caused by the S-ICD System User's Manual or labelling of the S-ICD System
- Type III: Not caused by the S-ICD System, but would not have occurred in the absence of the implanted S-ICD System.
- Type IV: Caused by a change in the patient's condition
- Type V: Not a clinical event (not an observation or a complication)

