10.4 Patient Death

Investigators should report any patient death to the Registry sponsor as soon as possible. If possible, the S-ICD System should be removed from the patient, and returned to Boston Scientific for analysis and the data related to the death recorded as appropriate in the database. If possible, a detailed death letter should also be provided to the Registry sponsor.

In the event that the S-ICD pulse generator or subcutaneous electrode cannot be removed, the S-ICD pulse generator should be interrogated prior to interment if possible. Remove the S-ICD from a deceased patient prior to cremation. The device battery may explode when exposed to extreme temperatures.

All patient deaths experienced during the Registry will be reported by the Registry sponsor to the appropriate regulatory agencies in line with individual countries' vigilance reporting requirements.

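### A death adjudicated as caused by the S-ICD, but without invasive intervention, is not counted in either complication-free rate

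*Combined protocol and SAP*

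**What the plan says.** The rule is spread over four sections of the combined protocol and SAP.

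- **5.3 Registry Endpoints.** The footnote to Endpoints 1 and 2 reads "Type I Complications will be considered to count towards the complication rate endpoints". Endpoint 1 is a simple percentage of the Registry population with an exact interval. Endpoint 2 is a Kaplan-Meier estimate at 360 days with a Peto standard error.
- **10.1 Clinical Event Definitions.** An observation is "A clinical event that does not result in invasive intervention"; a complication is an event that does result in one. The text adds: "Examples of such non-invasive intervention include, system reprogramming, antibiotic treatment of pocket infection, or change in medications". Among these definitions, death appears only as a criterion for a serious adverse event, and the endpoint footnote does not use that category.
- **10.2 Classification of Clinical Events.** "All clinical events will be categorized as observations or complications". Each event also receives a type from I to V; Type I means caused by the S-ICD System.
- **5.7 Missing Data.** "Time-to-event drop-outs will be censored, consistent with the Kaplan-Meier approach".

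All-cause mortality and all clinical events are listed separately as observational data in 3.2.1, and 5.5 provides for clinical event rates.

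**The concern.** The observation/complication split depends on what was done to the patient, not on what happened to the patient. An event that kills before anyone can operate, or that is treated only with drugs, falls on the observation side however grave it is. A revision for a displaced electrode lowers the complication-free rate; a device-caused death without surgery does not.

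Such deaths are conceivable. Section 9.1 lists "Failure to deliver therapy", infection and death among the risks, and 10.1 treats antibiotic therapy for a pocket infection as non-invasive.

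At stake is the meaning of the two complication endpoints. Readers will take a complication-free rate to exclude patients whom the device killed. An analyst who follows 5.3 and 10.1 literally would leave those patients in, and the resulting error always makes the rate look better.

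**Working it through.** **Step 1: follow one patient through the rules.** Suppose a death is adjudicated Type I and no invasive intervention took place.

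1. By 10.2 the event must be an observation or a complication; there is no third class.
2. By 10.1, without invasive intervention it is an observation.
3. By 5.3 only Type I complications count, so a Type I observation does not.
4. Endpoint 1: nothing removes the patient from the Registry population, so the patient is scored complication-free.
5. Endpoint 2: the patient has no event and follow-up ends at death. Kaplan-Meier practice and 5.7 lead to censoring at that date. No section states this for deaths, and none offers another treatment.

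**Step 2: reproduce the plan's own precision at n = 900** (Tables 1 and 2, section 5.6).

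- Table 1, 98%: the Clopper-Pearson interval for 882/900 is 96.86% to 98.81%, or −1.14/+0.81 points. The table gives −1.1/+0.8.
- Table 2, 90%: 1.96 × √(0.90 × 0.10 / 900) = 1.96 points. The table gives ±2.0.

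**Step 3: effect on Endpoint 1.** Each such death moves one patient from success to failure: 1/900 = 0.11 points.

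| Deaths counted as failures | Rate | Exact 95% interval |
|---|---|---|
| 0 | 98.00% | 96.86 to 98.81 |
| 1 | 97.89% | 96.72 to 98.72 |
| 2 | 97.78% | 96.59 to 98.64 |

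**Step 4: effect on Endpoint 2.** Assume 900 patients, 90 complications spread evenly over 360 days, k such deaths (mid-period for k = 1, otherwise spread evenly) and no other censoring. If the deaths count as events, the estimate is 1 − (90 + k)/900. If they are censored, it is the usual product of (1 − 1/number at risk) over the complications alone.

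For k = 1, with 45 complications before the death, 855 patients are at risk when it occurs. Censored: (855/900) × (809/854) = 89.99%. Counted: 809/900 = 89.89%.

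| k | Censored | Counted | Difference (points) |
|---|---|---|---|
| 1 | 89.99% | 89.89% | 0.11 |
| 2 | 89.99% | 89.78% | 0.21 |
| 5 | 89.97% | 89.44% | 0.53 |
| 9 | 89.95% | 89.00% | 0.95 |

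(Differences are taken before rounding.)

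**Step 5: how many such deaths?** The documents give neither a mortality rate nor a Type I share, so both are assumptions. Expected deaths = 900 × (1 − exp(−h × t)), with yearly hazard h and t in years.

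| h | Deaths by day 30 | Deaths by day 360 |
|---|---|---|
| 0.01 | 0.7 | 8.8 |
| 0.03 | 2.2 | 26.2 |
| 0.05 | 3.7 | 43.3 |

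If 2% to 20% of deaths are Type I and none of those involved invasive intervention, the expected number is 0.01 to 0.74 by day 30 and 0.2 to 8.7 by day 360. That is at most about 0.1 point on Endpoint 1, and about 0.0 to 1.0 point on Endpoint 2.

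**The case against.** The strongest reply is that this is a labelling gap with little practical effect. Section 5.0 makes the analyses descriptive, and no hypothesis test hangs on either rate. The deaths are not hidden: they enter all-cause mortality, clinical event rates and safety reporting. The expected shift in Endpoint 1 is close to nil. The upper end for Endpoint 2 needs 5% yearly mortality and a 20% Type I share together, and is still about half of the ±2.0 points in Table 2. All of this stands, and it sets the severity. It does not repair the two rates, because no listed analysis puts these deaths back into them.

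Four stronger readings are tempting, and the documents do not support them.

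- *That the plan expressly censors these deaths.* Neither 5.3 nor 10.1 mentions censoring, and 5.7 speaks of drop-outs. The phrase "is withdrawn including for reasons of death" is in 7.5, which governs annual follow-up after the first 360 days. Table 3 lists deaths and withdrawals on separate rows, and 8.0 does not name death among its withdrawal reasons. Censoring is the natural inference, no more.
- *That deaths from unshocked arrhythmia or pocket infection are bound to be lost this way.* Adjudicators might type the first as IV (a change in the patient's condition) and the second as III (not caused by the system, but impossible without it). Such deaths would stay outside the endpoints even after the fix. The point concerns only deaths adjudicated Type I.
- *That post-mortem removal decides whether a death counts.* Section 10.4 says "If possible, the S-ICD System should be removed from the patient", and 10.1 names explant as an invasive intervention. But removal after death is for device analysis and is not naturally an intervention resulting from the event.
- *That retrospective patients should enter the Endpoint 2 risk set only at enrolment.* That is a separate question. It would discard data since implant that 5.9 requires, and 5.9's mention of death leaves open whether such patients had to be alive to enrol.

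Adjudicators could in practice call a device-caused death a complication, but no written rule tells them to.

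**Conclusion.** The point holds as a minor one. For Endpoint 1 it follows directly from 5.3, 10.1 and 10.2: a Type I death without invasive intervention is scored as complication-free. For Endpoint 2 the censoring is inferred. A death following a Type I event that did lead to invasive intervention already counts, so the gap is confined to the remainder.

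The per-death size of about 0.11 points is arithmetic at n = 900, with Step 4's event pattern assumed for Endpoint 2. The number of such deaths rests entirely on the assumed mortality and Type I ranges. The case for changing the rule is the direction of the error and the gravity of the event, not a large numerical shift.

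**What to change.** Reword the 5.3 footnote along these lines: *Type I complications, and any Type I clinical event that led to death whether or not invasive intervention occurred, count towards Endpoints 1 and 2.* Then:

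- count the death as an Endpoint 1 failure if it occurs by day 30, and as an event at the date of death in Endpoint 2;
- adjudicate the type (I to V) of every death to day 360. The 4.4 minimum covers only endpoint-related events, and a death is not known to be one until it has been typed;
- also show both rates under the current footnote, for continuity.

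A sentence saying that post-mortem removal is not an invasive intervention is an optional clarification.

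The cost is one footnote, one extra line per endpoint, and typing about 9 to 43 deaths per 900 patients at the assumed 1% to 5% per year. Section 10.2 already asks for a type for every clinical event, and 5.9 already requires files on deaths for retrospective patients. No visits or tests are added. The downsides are a slightly less favourable rate and some deaths whose type stays uncertain, because device return and death letters are requested only where possible. The report should state how many.
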